8.5.3 STUDY DRUG ADMINISTRATION AND MONITORING

The study drug will be administered for up to 90 minutes daily for up to 3 days following randomization or until discontinuation of mechanical ventilation, whichever occurs first according to **Section 6.1.9**. See **Sections 6.1.6, 6.1.7, and 6.1.8** for information about study drug hold, interruption, and permanent discontinuation criteria.

Study Drug Dosing:

Subjects randomized to CO will be administered iCO at 200 ppm for 20 min as a “test dose” on each treatment day to determine in real-time each subject’s CFK equation-determined personalized dose. COHb levels will be measured before and after the 20 min test dose, and these two levels entered into the CFK equation calculator program to estimate DL_{CO} and compute the iCO dose to achieve a COHb level of 7% (target 6-8%) at 90 min. After the iCO dose is determined, subjects will be administered iCO at the CFK equation-determined personalized dose (200-500 ppm) but not to exceed 500 ppm or 90 min total (including test dose). Subjects randomized to placebo will be administered air.

Monitoring during Study Drug Administration:

Subjects will be monitored with continuous pulse oximetry, cardiac monitoring, and either intermittent (at least every 15 minutes) or continuous blood pressure monitoring (if an arterial line is in place) throughout the course of the 90-minute study drug treatment.

$SpCO$ and SpO_2 will be monitored continuously using a Masimo Rad-7 non-invasive pulse oximeter, and recorded at the time points specified in **Table 5**. COHb levels will be measured using an IL GEM Premier Co-oximeter and recorded at the time points specified below. Arterial or venous blood will be drawn for blood gas analysis prior to treatment and at the completion of study drug administration (90 min or earlier if discontinued prior to 90 min). If study drug treatment is discontinued prior to 90 min, all of the scheduled 90-minute measurements will be made and recorded at the time of study drug discontinuation. Ambient CO levels will be monitored continuously using a Dräger Pac 7000 CO detector, and recorded at the time points specified below.

Table 5. CO Monitoring During Treatment

| | ABG or VBG (pH, PCO_2 , PO_2) | FiO_2 | COHb level (IL GEM Premier co-oximeter) | CO Dose Adjustment (CFK calculator) | $SpCO$ (Masimo Rad-7) | SpO_2 (Masimo Rad-7) | Ambient CO Level (Dräger Pac CO detector) |
|--|------------------------------------|---------|---|-------------------------------------|-----------------------|------------------------|---|
|--|------------------------------------|---------|---|-------------------------------------|-----------------------|------------------------|---|

| Pre-treatment | X | X | X | | X | X | X |
|---------------|---|---|---|---|---|---|---|
| 20 min | | | X | X | X | X | X |
| 40 min | | | X | | X | X | X |
| 60 min | | | X | | X | X | X |
| 75 min | | | X | | X | X | X |
| 90 min* | X | X | X | | X | X | X |
| 180 min | | | X | | X | X | X |

*90 min or upon completion of study product if discontinued sooner than 90 min.

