3 OBJECTIVES AND ENDPOINTS

| OBJECTIVES | ENDPOINTS | JUSTIFICATION FOR ENDPOINTS |
|--|--|--|
| Primary | | |
| To evaluate the safety and accuracy of a CFK equation-based personalized iCO dosing algorithm in patients with pneumonia and/or sepsis-induced ARDS. | 
1. Safety of iCO, defined by the incidence of pre-specified administration-related AEs and SAEs.
 
Administration-related SAEs are: 1) myocardial infarction; 2) stroke; 3) new onset arrhythmia requiring DC cardioversion; 4) worsening hypoxemia^{1,2}; 5) COHb $\geq 10\%$; and 6) increase in lactate by ≥ 2 mmol/L.
 
2. Accuracy of the CFK equation-based personalized iCO dosing algorithm. This will be assessed by comparing the measured COHb level at 90 minutes and the target COHb level of 6-8%.
 | 
1. Safety of iCO: These administration-related SAEs were used in our prior Phase I fixed-dose iCO trial and are SAEs that could potentially occur if there were decreased delivery of oxygen. A COHb level $\geq 10\%$ was chosen as an administration-related SAE as the goal COHb is 6-8%.
 
2. Accuracy of personalized iCO dosing approach: The accuracy of the iCO dosing algorithm to achieve the target COHb level (6-8%) will be evaluated.
 |
| Secondary | | |
| To determine the effect of low dose iCO therapy on clinical outcomes in patients with | 1. Lung Injury Score (LIS) on days 1-5 and day 7 2. PaO ₂ /FiO ₂ on days 1-5 and day 7 | LIS, PaO ₂ /FiO ₂ , OI, and Vd/Vt have been shown to correlate with VFDs and |

| OBJECTIVES | ENDPOINTS | JUSTIFICATION FOR ENDPOINTS |
|--|---|---|
| pneumonia and/or sepsis-induced ARDS. | 3. Oxygenation index (OI) on days 1-5 and day 7 4. Dead space fraction (Vd/Vt) on days 1-3 and day 7 5. Sequential Organ Failure Assessment (SOFA) scores on days 1-5, 7, 14, and 28 6. Ventilator-free days (VFDs) to day 28 7. ICU-free days to day 28 8. Hospital-free days to day 60 9. Hospital mortality to days 28 and 60 10. Neurocognitive function at 3 and 6 months | mortality in prior ARDS studies. |
| Exploratory | | |
| To examine the effects of low dose iCO therapy on biologic readouts in patients with pneumonia and/or sepsis-induced ARDS. | Blood and urine biomarkers of mitochondrial dysfunction (mtDNA), inflammasome activation (IL-18) and necroptosis (RIPK3). Lipid mediators (LM) and specialized pro-resolving mediators (SPMs). | Our preliminary data suggest that CO may modulate these biomarkers. |

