6.1.7 INTERRUPTION OF DOSING DURING STUDY DRUG ADMINISTRATION

Subjects will have blood drawn for measurement of COHb levels prior to study drug treatment and 20 min, 40 min, 60 min, 75 min, 90 min, and 180 min after the start of study drug treatment. It is anticipated that COHb levels will not exceed the target range of 6-8% given the impaired diffusion capacity in ARDS patients and CFK equation-determined personalized iCO dosing algorithm. However, the following parameters will be used to shorten the 90 minute treatment duration should CO uptake be higher than anticipated:

The study drug will be stopped prior to 90 minutes:

1. If the measured COHb level is > 8% at any time during study drug treatment.
2. If the investigator, attending physician, the patient, or their surrogate decides that the study drug should be discontinued.

If COHb levels unexpectedly exceed our target level, in addition to discontinuation of the study drug, subjects will be placed on 100% O₂ to accelerate CO elimination until COHb levels normalize.

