9.4.2 ANALYSIS OF THE PRIMARY SAFETY ENDPOINT(S)

We hypothesize that iCO will be safe and well-tolerated and that our iCO dosing algorithm will be accurate

in achieving target COHb levels.

We will examine all AEs including pre-specified administration-related AEs by the type of event, as well as by body system class, and will report proportions and 95% CI. We will compare the occurrence of specific AEs in each arm by the χ^2 test, and the number of AEs per patient in each arm by the Wilcoxon-Mann-Whitney test.

COHb levels will be summarized descriptively reporting mean, standard deviation, median, minimum, and maximum at each time point, each day, by treatment arm. The mean difference between predicted and measured COHb levels with 95% confidence intervals will be presented for the iCO group. Repeated measures analysis of variance (ANOVA) will be used to assess the effects of treatment, time (over 3 days), and the interaction between time and treatment for 90-minute COHb levels. ANOVA will be repeated to assess the effects of treatment, time (over 3 days), entry criteria (ARDS/Sepsis vs. Non-ARDS/Sepsis Pneumonia vs. Non-ARDS/non-Sepsis Pneumonia), and two-way/three-way interactions of time, treatment and entry criteria. We will also compare the occurrence of COHb $\geq 10\%$ in each arm by the χ^2 test.

Accuracy of the CFK equation-based personalized iCO dosing algorithm to achieve target COHb levels will also be analyzed by Spearman correlation and Bland-Altman plots using measured vs. predicted COHb levels and modeled using linear or non-linear regression.

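### COHb drawn when dosing stops early is recorded as the 90-minute value, and the primary 6-8% accuracy comparison and the ANOVA do not separate these shortened sessions

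*Combined protocol and SAP*

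**What the plan says.** Section 8.5.3 deals with treatment that ends before 90 minutes: "all of the scheduled 90-minute measurements will be made and recorded at the time of study drug discontinuation". The note to the 90-minute row of Table 5, a row in which COHb is marked, says the same: "90 min or upon completion of study product if discontinued sooner than 90 min".

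Section 6.1.7 gives two grounds for stopping early. One depends on the outcome itself: "If the measured COHb level is > 8% at any time during study drug treatment". The other need not: "If the investigator, attending physician, the patient, or their surrogate decides that the study drug should be discontinued".

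The dosing program is meant to "compute the iCO dose to achieve a COHb level of 7% (target 6-8%) at 90 min" (Section 8.5.3). Section 3 defines the accuracy endpoint accordingly: "This will be assessed by comparing the measured COHb level at 90 minutes and the target COHb level of 6-8" per cent. Section 9.4.2, repeated in Section 9.4.5, plans a repeated measures ANOVA of treatment, time "and the interaction between time and treatment for 90-minute COHb levels". It adds: "The mean difference between predicted and measured COHb levels with 95% confidence intervals will be presented for the iCO group". That sentence names no time point, and neither does the one on Spearman correlation and Bland-Altman plots.

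Sections 9.3 and 9.4 give no rule for shortened sessions. The missing-data text in Section 9.4.3 concerns missed visits, withdrawal and death.

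**The concern.** The algorithm is designed to be right at 90 minutes, and COHb is still rising until then. A reading taken at 40 or 60 minutes and stored in the 90-minute field measures a shorter exposure. If the field is analysed as labelled, a session stopped for a reason unrelated to dosing looks like algorithm error, and a session that was overshooting can look like a success if it is stopped while passing through the target band. Both errors fall on a primary endpoint. If the handling is left until analysis, it will be chosen by people who can see COHb values, and these largely reveal the treatment arm.

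**Working it through.** **1. The plan's own precision figure.** Section 9.2 uses SD 0.6, 24 iCO subjects and 8% dropout (24 x 0.92 = 22.1, so about 22). The 95% CI half-width is t(0.975, n-1) x SD / sqrt(n).
- n = 24: 2.069 x 0.6 / 4.899 = 0.253
- n = 22: 2.080 x 0.6 / 4.690 = 0.266

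The probability that the half-width is at most 0.5 is about 1.00, and 0.1467 ± 0.5 gives -0.353 to 0.647. The stated figures reproduce and are not in dispute.

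**2. What an early reading looks like.** Table 4, predicted COHb (%) at constant dose; the 75-minute values are linear interpolations between 60 and 90 minutes.

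| Dose row | 40 min | 60 min | 75 min | 90 min |
|---|---|---|---|---|
| 400 ppm | 4.0 | 5.3 | 6.15 | 7.0 |
| 500 ppm | 4.8 | 6.5 | 7.55 | 8.6 |

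- False miss: on the 400 ppm row the course is exactly on target. A 40-minute stop is filed 3.0 points low (4.0 - 7.0) and a 60-minute stop 1.7 points low (5.3 - 7.0). Both fall outside 6-8%.
- False hit: on the 500 ppm row a 60-minute stop is filed as 6.5%, in range, on a course to 8.6%.

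Trial sessions start with 20 minutes at 200 ppm, so these values are approximate. As a rough check, take a straight line from 1.6% at 20 minutes (200 ppm row) to the 90-minute value.
- Heading for 7.0%: 1.6 + (20/70) x 5.4 = 3.1% at 40 minutes and 1.6 + (40/70) x 5.4 = 4.7% at 60 minutes.
- Heading for 8.6%: 1.6 + (40/70) x 7.0 = 5.6% at 60 minutes and 1.6 + (55/70) x 7.0 = 7.1% at 75 minutes.

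The shortfalls become somewhat larger and the false-hit window moves later. Both errors remain possible.

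**3. Effect of a single stop.** Let one session among n be filed d = 3.0 points low, with SD 0.6 otherwise. The mean shift is -d/n, and the expected sample variance is 0.6² + d²/n.
- n = 24 (one treatment day): shift -3.0/24 = -0.125; SD = sqrt(0.36 + 0.375) = 0.86.
- n = 72 (24 subjects x 3 days): shift -3.0/72 = -0.042; SD = sqrt(0.36 + 0.125) = 0.70.

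The Phase Ia mean difference was 0.1467. These shifts apply to the 90-minute COHb field. They carry over to measured minus predicted only if the fixed 90-minute prediction is used. In that case the Bland-Altman limits for n = 24 would widen from ±1.96 x 0.60 = ±1.2 to ±1.96 x 0.86 = ±1.7.

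**4. A range of assumed stop rates.** The documents give none, so q = 5%, 10% and 20% are assumptions, with all stops at 40 minutes (d = 3.0) or all at 60 (d = 1.7). The mean shift is -q x d and the SD is sqrt(0.36 + q(1-q)d²). With 90-minute COHb centred at 7 + 0.1467 and SD 0.6, the in-range share without stops is about 0.895. With stopped sessions filed out of range it is 0.895 x (1-q).

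| q | Mean shift (60 / 40 min) | SD (60 / 40 min) | Half-width, n = 22 | In-range share |
|---|---|---|---|---|
| 5% | -0.09 / -0.15 | 0.71 / 0.89 | 0.31 / 0.39 | about 85% |
| 10% | -0.17 / -0.30 | 0.79 / 1.08 | 0.35 / 0.48 | about 81% |
| 20% | -0.34 / -0.60 | 0.91 / 1.34 | 0.40 / 0.59 | about 72% |

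**5. Overshoot stops.** A simulation used the Table 4 curve shape, an assumed baseline of 0.9% and stops at 40, 60 or 75 minutes when COHb exceeds 8%. At SD 0.6, about 0.05% of sessions stop before 90 minutes for this reason and the mean and SD barely change (SD 0.599 to 0.597). The share reaches 2.2% at SD 1.0 and 9.1% at SD 1.5, but no passage supports SDs that large. A session stopped above 8% is out of range under either label, so the in/out count does not change.

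**The case against.** Drawing blood when dosing ends is a sensible collection rule. Once gas is stopped no full-exposure 90-minute value exists, and after an overshoot Section 6.1.7 moves the subject to 100% oxygen, so a draw at clock minute 90 would be less informative. This stands: the draw should stay, and only its label in the analysis is at fault.

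A reader might infer that the mean difference and the Bland-Altman limits are necessarily biased. The documents do not support that. Section 9.4.2 names no time point for the prediction, and Section 2.2.9 shows that the program gave predictions at 60, 75 and 90 minutes in Phase Ia. If each reading is matched to its own time, those analyses are clean. The 6-8% comparison and the ANOVA remain exposed.

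A reader might also infer that the label hides high COHb values. It does not. Overshoot truncation is negligible at the planning SD and follows from stopping, not from labelling. The safety event of COHb at or above 10% counts any protocol-specified measurement (Section 8.7.3).

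Finally, stops may be few. Hold criteria are checked before each dose, a study physician is at the bedside (Section 6.1.1), and Phase Ia had no administration-related AEs. This does not show that stops will be rare, but it does mean that the sizes above are illustrations. Under the 5% and 10% assumptions the CI half-width also stays inside the planned 0.5.

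**Conclusion.** The point holds as a fault in a stated rule. Followed as written, it places readings from shorter exposures in the field used for the primary 6-8% comparison and for the ANOVA, and it can produce both false misses and false hits. The main problem is incomplete exposure from stops for reasons other than COHb above 8%.

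The size depends on how many sessions are cut short, which the documents do not say. One 40-minute stop shifts the mean by -0.125 among 24 sessions or -0.042 among 72, with the SD at about 0.86 or 0.70 in place of 0.60. These figures rest on the planning SD and on constant-dose Table 4 values that only approximate trial sessions. Effects on measured-minus-predicted results are conditional on the pairing used. The sample-size calculation stands, and nothing here bears on when dosing should stop. A correction to the analysis plan before COHb data are reviewed is warranted.

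**What to change.** Leave the stopping rule and the end-of-dosing draw unchanged, and amend the analysis text in Sections 9.4.2 and 9.4.5.
- Analyse an end-of-dosing reading at its actual elapsed time and compare it with the CFK prediction for that time. State this pairing for the mean difference, correlation, regression and Bland-Altman analyses.
- Do not treat such a reading as a 90-minute value in the ANOVA or in the 6-8% comparison.
- Count sessions stopped for COHb above 8% as not in target.
- Report sessions stopped for other reasons separately, by reason. Show the in-target share twice: with these sessions counted as not in target, and restricted to full 90-minute sessions. Excluding them alone would not be enough: the administering physician is unblinded and sees serial COHb, so a discretionary stop may itself reflect rising COHb.

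The cost is small: a few fewer 90-minute values, some analysis wording and possibly one case report form field. Section 6.4 records time and duration of treatment but does not list the reason for an interruption, so that field should be confirmed or added.

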8.6 POST-TREATMENT ASSESSMENTS

8.6.1 STUDY DAYS 4, 5, AND 7

If the subject remains hospitalized, the following assessments will be completed. See **Section 8.1** for descriptions of study assessments.

- Review interval medical events, ventilator settings, vital signs, and concomitant medications
- Review EKG on study day 7, and other days if available
- Review chest X-ray on study day 7, and other days when available
- Urine and blood collection for research labs on study day 5
- ABG or VBG when available
- SpO₂
- Lung injury score (LIS)
- Dead space fraction (Vd/Vt) on day 7
- Obtain Glasgow Coma Score (GCS), SOFA score, and Richmond Agitation Sedation Scale (RASS)
- The following lab values will be recorded if available and requested by treating physician: CBC, basic metabolic panel, PT/PTT/INR, Serum CK, AST, ALT, Albumin, Total Protein, and Lactate
- Collection of blood for bilirubin if not drawn by the clinical team
- Vasopressors and inotropes review
- Fluid intake and output (most recent 24 hour value) or mean hourly value for most recently available period on days 4 and 5
- Renal Replacement Therapy Status
- Adverse event review
- Microbial results when available
- Discarded BAL and plasma samples when available

8.6.2 STUDY DAY 14

If the subject remains hospitalized, the following assessments will be completed. See **Section 8.1** for descriptions of study assessments.

- Ventilator Parameters Assessment
- SOFA Score
- GCS
- SpO₂ when available
- Blood collection for total bilirubin if not drawn by the clinical team

- ABG or VBG when available
- CBC and basic metabolic panel when available
- Vasopressors and Inotropes Review
- Renal Replacement Therapy Status
- Microbiological results when available

8.6.3 STUDY DAY 28

If the subject remains hospitalized, the following assessments will be completed. See **Section 8.1** for descriptions of study assessments.

- Review interval medical events
- Obtain GCS and SOFA score at Day 28 or on discharge date
- Collection of blood for total bilirubin if not drawn by the clinical team
- CBC and basic metabolic panel if available
- Microbial results when available
- Vasopressors and Inotropes Review
- Renal Replacement Therapy Status
- Discharge, ventilator, and vasopressor status

If the subject has been discharged home or to a long-term acute care facility, the subject will be contacted by telephone to:

- Obtain vital status

8.6.4 STUDY DAY 60

If the subject remains hospitalized, the following assessments will be completed. See **Section 8.1** for descriptions of study assessments.

- Discharge, ventilator, and vasopressor status

If the subject has been discharged home or to a long-term acute care facility, the subject will be contacted by telephone to:

- Obtain vital status

8.6.5 MONTH 3 AND 6 ASSESSMENTS

Subjects will be contacted by phone at 3 and 6 months for the following assessments. See **Section 8.1** for descriptions of study assessments:

- Obtain vital status
- Neurocognitive testing- Telephone versions of the Montreal Cognitive Assessment (MoCA) and Hayling sentence completion test

8.7 ADVERSE EVENTS AND SERIOUS ADVERSE EVENTS

8.7.1 DEFINITION OF ADVERSE EVENTS (AE)

Adverse event means any untoward medical occurrence associated with the use of an intervention in humans, whether or not considered intervention-related (21 CFR 312.32 (a)).

8.7.2 DEFINITION OF SERIOUS ADVERSE EVENTS (SAE)

An adverse event (AE) or suspected adverse reaction is considered "serious" if, in the view of either the investigator or sponsor, it results in any of the following outcomes:

- results in death;
- is life threatening (places the subject at immediate risk of death from the event as it occurred);
- requires inpatient hospitalization or prolongation of existing hospitalization;
- results in a persistent or significant disability/incapacity;
- results in a congenital anomaly/birth defect; or
- any other adverse event that, based upon appropriate medical judgment, may jeopardize the subject's health and may require medical or surgical intervention to prevent one of the outcomes listed above.

Organ failures related to ARDS or the patient's underlying condition that are systematically captured by the protocol should not be reported as adverse events **unless they are considered to be study related**. If the suspected adverse reaction is unexpected, it will be classified as a serious unexpected suspected adverse reaction (SUSAR).

8.7.3 DEFINITION OF ADMINISTRATION RELATED ADVERSE EVENTS

For this trial, a subset of adverse events will be considered to be "administration related adverse events". These "administration related adverse events" will by definition be considered suspected adverse reactions. These events are:

- Acute MI* within 48 hours of study drug administration
- Acute stroke** within 48 hours of study drug administration
- New onset atrial or ventricular arrhythmia requiring DC cardioversion within 48 hours of study drug administration
- Increased oxygenation requirements defined as: an increase in FiO_2 of ≥ 0.2 **AND** increase in PEEP $\geq 5 \text{ cm H}_2\text{O}$ within 6 hours of study drug administration
- Increase in any protocol-specified measurement of COHb $\geq 10\%$
- Increase in lactate by $\geq 2 \text{ mmol/L}$ within 6 hours of study drug administration

* Acute MI is defined below according to the Executive Group on behalf of the Joint European Society of Cardiology (ESC)/American College of Cardiology (ACC)/American Heart Association (AHA)/World Heart Federation (WHF) Task Force for the Universal Definition of Myocardial Infarction¹⁴⁴. We will also rely upon subspecialty consultation to confirm the presence or absence of an acute MI.

Acute myocardial infarction is defined as acute myocardial injury with clinical evidence of acute myocardial ischemia and with detection of a rise and/or fall of cardiac troponin values with at least 1 value above the 99th percentile upper reference limit and at least 1 of the following:

- Symptoms of myocardial ischemia;
- New ischemic ECG changes;
- Development of pathological Q waves;

- Imaging evidence of new loss of viable myocardium or new regional wall motion abnormality in a pattern consistent with an ischemic etiology;
- Identification of a coronary thrombus by angiography or autopsy (not for types 2 or 3 MIs).

** Acute stroke is defined as an acute neurological deficit attributed to an acute focal injury of the central nervous system by a vascular cause, including cerebral infarction, intracerebral hemorrhage, and subarachnoid hemorrhage based on neuropathological, neuroimaging, and/or other clinical evidence of permanent injury¹⁴⁵. We will also rely upon subspecialty consultation to confirm the presence or absence of an acute stroke.

